8.7 Subgroup analyses

Analysis of efficacy profile by age in order to characterize a potential benefit of the drug in elderly population is planned. Exploratory efficacy subgroup analyses according to genetic risk, the refractory status to prior therapies such as bortezomib, lenalidomide/thalidomide, last prior therapy, IMiD therapy and PIs are planned. No other specific subgroup analysis is planned for efficacy. However, the influence of the study strata and other prognostic factors on the efficacy endpoints will be studied in the multivariate analysis.

No formal statistical allowance will be made for multiple subgroup investigations, but any apparent subgroup interactions will be interpreted appropriately in a cautious way.

Analysis of safety profile by age, gender and body mass index (BMI) will be provided as specified in section 12.7.

Handling of multicenter data

No randomization or stratification by center will be performed as the sample size by center is expected to be low. Further “by center” analyses may be performed upon request if appropriate.

Handling of multiple comparisons

Single comparison of PFS between arm A and B will be made for the primary endpoint. No adjustment, except for the sequential OS analyses described in section 5.1, will be made for multiple comparisons in secondary analyses.

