5 SAMPLE CONSIDERATIONS

5.1 Randomization

Patients fulfilling all eligibility criteria will be stratified according to the Eastern Cooperative Oncology Group (ECOG) Performance Status (PS) score (0 and 1 vs. 2) and Durie-Salmon stage at diagnosis (I/II vs. III) and then randomized using a 2:1 randomization procedure to Arm A (plitidepsin in combination with dexamethasone) or Arm B (dexamethasone alone). Randomization will be used to avoid bias in the assignment of patients to treatment, and to increase the likelihood that known and unknown patient attributes (e.g., demographics and baseline characteristics) are evenly balanced across treatment groups.

Randomization of patients should occur as close in time as possible before administration of the first dose of study drug(s) and must occur within 7 days of the patient receiving the first dose of study treatment. The randomization number and treatment code will be assigned after phoning into the Interactive Voice Response System (IVRS).

On the basis of the patient identification and stratum information, the IVRS will assign a treatment code, which will dictate the treatment assignment for that patient.

Patients will be assigned to each group by strata random list, so that a patient will have a two-thirds chance of getting Arm A (plitidepsin in combination with dexamethasone) and a one-third chance of getting Arm B (dexamethasone alone). The random permuted blocks method will be used; the size of the blocks in the randomization list will be fixed and not accessible to investigators. To select the blocks, a uniform (0, 1) variable with a random seed will be used.

5.2 *Sample size*

The number of patients randomized in the trial has been calculated based on PFS estimates obtained from the previous phase II study (APL-B-014-03).

1. **Arm A** (plitidepsin plus dexamethasone combination): approximately 167 patients.
2. **Arm B** (dexamethasone single agent): approximately 83 patients.

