Approximately 210 progression or death events would be needed in this trial to detect a HR of 0.625 in favor of the combination arm (equivalent to an increase of 60% in PFS, i.e., from 10 to 16 weeks, 12 to 19.2 weeks, 16 to 25.6 weeks) with 90% power and 1-sided 2.5% significance level. As a preliminary hypothesis, it is estimated that up to 250 randomized patients will be needed to achieve the 210 events in 24-30 months. For the calculation of the number of events needed, the target HR to be detected is 0.625, with 90% power and 2.5% unilateral significance level. This is equivalent to a minimum 60% increase in PFS, which has been considered statistically and clinically significant by the Sponsor.

An early futility analysis will be performed with the data collected when 40 patients in Arm A are evaluable for response. A response rate (IMWG criteria) of at least 30% (twelve or more responses by IRC review) will be taken as threshold for continuation of the study. A minimum response rate of 30% has been considered as clinically significant in this setting. This result will ensure that the lower limit of the exact binomial 95% Confidence Interval for the response rate will be greater than 15% (95% CI in case of 12 responses would be 16.6% - 46.5%).

However, the efficacy and safety information from all randomized patients in both arms at that time will be used by the independent data monitoring committee (IDMC) to provide the Sponsor with a recommendation for further study conduct.

The final PFS analysis will be performed when at least 210 progression or death events are observed.

An interim analysis of OS will be performed concomitantly with the final PFS analysis. In addition, a final analysis of OS will be performed when 80% of death events (approximately 200 death events) have occurred or 24 months after the inclusion of the last patient, whichever occurs first. At the interim OS analyses, the significance level determined by the O'Brien-Fleming (1) boundary with overall 2.5% 1-sided significance level will be used.

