6.2 Efficacy analysis methods

6.2.1 Primary endpoint

For the evaluation of the main primary endpoint (PFS), the "All Randomized Patients" population, the data from the Independent Review Committee (IRC), and the unstratified log-rank test will be used to compare both treatment arms. The final PFS analysis will be performed when at least 210 progression or death events are observed.

Cox regression will be used to calculate the risk reduction in PFS

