Univariate evaluation of the influence of different prognostic factors on the main efficacy endpoints will be performed by using the following covariates: Gender, age, baseline ECOG, Body Surface Area (BSA), MM type (i.e.: IgG, IgA, light chain myeloma, non-secretory), number of prior lines of anticancer treatment, status (relapsed *vs.* relapsed/refractory) refractory status to bortezomib, lenalidomide/thalidomide prior therapy, refractory status to last prior therapy, refractory status to IMiD therapy, refractory status to PIs therapy, genetic risk, previous SCT, time from diagnosis to randomization, time from last progression before randomization, International Staging System, Durie-Salmon stage, bone marrow plasma cells, bone lytic lesions (Y/N), plasmacytomas at baseline (Y/N), number of lesions at baseline, sum of the dimensions of plasmacytomas, creatinine (≥ 2 mg/dl *vs.* < 2 mg/dl), LDH, hemoglobin and corrected serum calcium (>11.5 mg/100ml *vs.* ≤ 11.5 mg/100ml).

Exploratory subgroup analyses will be performed by means of logistic regression, Kaplan-Meier analysis and Cox regression. The different subgroup analyses will be summarized by means of Forest plots.

Cox proportional hazard models for PFS and OS and logistic regression models for RR will include the prognostic factors specified for the univariate analysis. More relevant and explanatory covariates from the univariate analysis will be included in the multivariate analyses (p-value < 0.10). Prognostic factors with more than 10% missing values will be excluded in the multivariate analyses.

The analyses above mentioned will be also performed for the sensitivity analysis of PFS with confirmation of PD by IRC.

In addition, and in order to check if there are differences in the main efficacy endpoint between different continents/geographical areas, multivariate analyses of PFS by IRC, adding region as a covariate, will be performed. The variable “region” will be created with four categories (Europe, Asia, Oceania, and USA) and then three Cox regressions will be performed.

- 1) PFS by IRC with arm, region and interaction term.
- 2) PFS by IRC with arm and region as main effects.
- 3) Full model selected in the multivariate analysis of PFS by IRC, including region as variable.

Symmetry of evaluations.

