11.3.6 Efficacy analysis by age

If there is a group of patients with scarce percentage of patients (i.e. 5%), it will be joined to the nearest group of age. Age ≥ 85 to Age 75-84, age 75-84 to age 65-74 and age 65-74 to age 18-64.

Table 11.3.6.1 PFS (Independent Review assessment and “All Randomized Patients” population) by age

Age		Arm A	Arm B	Parameter	p-value
Age 18-64	N				
	Events				
	Censored				
	Median PFS			Log-Rank: HR (95% CI) :	LR: HR:
	PFS at 6 months			Diff:	
Age 65-74	N				
	Events				
	Censored				
	Median PFS			Log-Rank: HR (95% CI) :	LR: HR:
	PFS at 6 months			Diff:	
Age 75-84	N				
	Events				
	Censored				
	Median PFS			Log-Rank: HR (95% CI) :	LR: HR:
	PFS at 6 months			Diff:	
Age ≥ 85	N				
	Events				
	Censored				
	Median PFS			Log-Rank: HR (95% CI) :	LR: HR:
	PFS at 6 months			Diff:	

Kaplan-Meier plot will be also shown (Figure 11.3.6.1a/b/c/d)

Table 11.3.6.2 PFS (Investigator Assessment and “All Randomized Patients” population) by age

Age		Arm A	Arm B	Parameter	p-value
Age 18-64	N				
	Events				
	Censored				
	Median PFS			Log-Rank: HR (95% CI) :	LR: HR:
	PFS at 6 months			Diff:	
Age 65-74	N				
	Events				
	Censored				
	Median PFS			Log-Rank: HR (95% CI) :	LR: HR:
	PFS at 6 months			Diff:	
Age 75-84	N				
	Events				
	Censored				
	Median PFS			Log-Rank: HR (95% CI) :	LR: HR:
	PFS at 6 months			Diff:	
Age ≥85	N				
	Events				
	Censored				
	Median PFS			Log-Rank: HR (95% CI) :	LR: HR:
	PFS at 6 months			Diff:	

Kaplan-Meier plot will be also shown (Figure 11.3.6.2a/b/c/d)

Table 11.3.6.3 OS (“All Randomized Patients” population) by age

Age		Arm A	Arm B	Parameter	p-value
Age 18-64	N				
	Events				
	Censored				
	Median OS			Log-Rank: HR (95% CI) :	LR: HR:
	OS at 12 months			Diff:	
	OS at 24 months			Diff:	
Age 65-74	N				
	Events				
	Censored				
	Median OS			Log-Rank: HR (95% CI) :	LR: HR:
	OS at 12 months			Diff:	
	OS at 24 months			Diff:	
Age 75-84	N				
	Events				
	Censored				
	Median OS			Log-Rank: HR (95% CI) :	LR: HR:
	OS at 12 months			Diff:	
	OS at 24 months			Diff:	
Age ≥85	N				
	Events				
	Censored				
	Median OS			Log-Rank: HR (95% CI) :	LR: HR:
	OS at 12 months			Diff:	
	OS at 24 months			Diff:	

Kaplan-Meier plot will be also shown (Figure 11.3.6.3a/b/c/d).

Table 11.3.6.4 Response rate by IMWG (Independent Review assessment and “All Randomized Patients” population) by age

Age	Response	Arm A		Arm B	
		N	%	N	%
Age 18-64	sCR CR VGPR PR MR SD PD Unknown*				

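### The PFS and OS subgroup tables give a p-value inside every subgroup and specify no treatment-by-subgroup test, except a separate model for region (exploratory output, minor)

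*SAP*

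**What the plan says.** SAP 8.7 plans an efficacy analysis by age, aimed at benefit in older patients. It adds exploratory analyses by genetic risk and by refractory status to bortezomib, lenalidomide/thalidomide, last prior therapy, IMiDs and proteasome inhibitors (PIs). It makes no multiplicity allowance and says that "any apparent subgroup interactions will be interpreted appropriately in a cautious way". It does not say how an interaction would be identified.

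On method, SAP 6.2.3 says: "Exploratory subgroup analyses will be performed by means of logistic regression, Kaplan-Meier analysis and Cox regression". Results are to be summarised in forest plots. No interaction term is named for these factors. For region, the same section does name one: "PFS by IRC with arm, region and interaction term".

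The shells apply this as follows:
- **PFS and OS tables, 11.3.6 to 11.3.11.** Each subgroup has its own log-rank result, HR with 95% CI, and two p-values (LR and HR). There are up to four age bands, three genetic-risk groups, four lenalidomide/thalidomide/bortezomib groups, and two groups each for last prior therapy, IMiD and PI. No table has an arm-by-factor row.
- **Response-rate tables in the same sections.** These show counts, proportions and exact CIs, without p-values.
- **Univariate tables, 11.3.4.8.** Each factor has one p-value column, footnoted only as Cox or logistic regression. The SAP does not say which term is tested.

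**The concern.** A p-value computed inside a subgroup asks whether the effect there differs from none. It does not ask whether the effect differs from that in the other subgroups. With a common HR, within-subgroup significance depends mainly on how many events the subgroup holds. A table showing significance in one row and not in another therefore invites a conclusion about differential benefit that it cannot support. This matters most for age, where the stated aim is to describe benefit in older patients: an age band with few events will tend to look negative even if it benefits equally. The promise of cautious interpretation gives the reader no statistic to be cautious with.

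**Working it through.** **Inputs from the documents.** SAP 5.2: "Approximately 210 progression or death events would be needed in this trial to detect a HR of 0.625 in favor of the combination arm", "with 90% power and 1-sided 2.5% significance level". SAP 5.1: patients are "randomized using a 2:1 randomization procedure to Arm A", so the Arm A share is 2/3. SAP 6.2.1: the "unstratified log-rank test will be used to compare both treatment arms"; SAP 11.3.2 makes the unstratified test the default in the tables.

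**Assumption.** The share of events in each subgroup is not in the documents. The splits below are illustrative.

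**1. Reproduce the plan's figure.** Schoenfeld: d = (1.960 + 1.282)² / [(2/3)(1/3)(ln 0.625)²] = 10.507 / (0.2222 × 0.2209) = 214.05, rounded up to 215. This is within 3% of 210. Power at 210 events: Φ(0.470 × √(210 × 2/9) − 1.96) = Φ(3.211 − 1.96) = 89.4%. The approximation agrees with the plan.

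**2. Power inside a subgroup with share s and the same HR.** Power = Φ(0.470 × √(210 × s × 2/9) − 1.96). For shares of 45%, 35% and 20% this gives Φ(2.154 − 1.96) = 57.7%, Φ(1.900 − 1.96) = 47.6% and Φ(1.436 − 1.96) = 30.0%.

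**3. Chance of a mixed pattern** (at least one subgroup significant and at least one not). Subgroups of one factor are disjoint, so their results are treated as independent and P(mixed) = 1 − P(all) − P(none). For 45/35/20:
- P(all) = 0.577 × 0.476 × 0.300 = 8%
- P(none) = 0.423 × 0.524 × 0.700 = 16%
- P(mixed) = 76%

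| Assumed split (%) | Power in each (%) | All sig. | None sig. | Mixed, HR 0.625 | Mixed, HR 0.80 |
|---|---|---|---|---|---|
| 50/50 | 62, 62 | 39% | 14% | 47% | 31% |
| 70/30 | 77, 42 | 32% | 14% | 54% | 31% |
| 45/35/20 | 58, 48, 30 | 8% | 16% | 76% | 36% |
| 25/25/25/25 | 36 each | 2% | 17% | 82% | 39% |
| 40/25/20/15 | 53, 36, 30, 24 | 1% | 16% | 83% | 39% |

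At HR 0.80 the figures fall because usually no subgroup is significant. A more uneven two-group split raises the figure at HR 0.625: 90/10 gives 74%.

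**4. A small age band.** SAP 11.3.6 merges sparse age bands, giving 5% as the example. A band holding 5% of events has 11% power; a band holding 10% has 17%.

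**5. The alternative.** One arm-by-factor test at two-sided 5% signals falsely in about 5% of trials per factor when the effect is uniform. For at least one of six independent factors the chance is 1 − 0.95⁶ = 26%.

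**6. Power of that alternative, equal halves.** SE of the log ratio of HRs = √[2 / (105 × 2/9)] = 0.293. For a ratio of 0.5: Φ(0.693/0.293 − 1.96) = 66%. For a ratio of 0.625: Φ(0.470/0.293 − 1.96) = 36%.

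**The case against.** The SAP presents these as exploratory analyses, disclaims multiplicity control and promises caution. Its revision history describes the age analyses as supportive, added to follow a geriatric guideline. Each PFS and OS subgroup already shows an HR with its CI, and forest plots are planned, so a careful reader can judge consistency by eye. Sparse age bands are merged. Three of the six factors have only two groups, where a mixed pattern is roughly a coin toss for moderate splits. An interaction test has low power, and a non-significant one could be misread as proof of uniformity.

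Most of this stands, and it limits the point to a minor one. It does not supply the missing test, and the SAP already uses the right method for region.

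Some stronger readings are tempting but unsupported:
- **That the SAP has no interaction test at all.** It has one, for region.
- **That the whole of 11.3.6 to 11.3.11 is affected.** The response-rate tables there print no p-values.
- **That a uniform effect will usually look mixed in every table.** This holds for the three- and four-group splits if the true HR is near 0.625. It does not hold for an evenly split two-group factor, nor at HR 0.80.
- **That the sponsor will infer differential benefit from such a pattern.** Nothing in the SAP says so.
- **That the oldest band will be the smallest.** The documents give no age distribution.
- **That the change would remove chance HRs above 1.** With HR 0.625 throughout, at least one subgroup HR exceeds 1 in about 12% of trials for the 45/35/20 split and 20-24% for four groups. Those HRs would still be printed.

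**Conclusion.** The point holds for the PFS and OS subgroup tables. They print within-subgroup p-values for six factors with no treatment-by-subgroup test, and the p-value in 11.3.4.8 is not defined as one. At the design effect, a uniform benefit gives a mixed pattern in about 47-54% of trials for a two-group factor (50/50 to 70/30), 76% for three groups (45/35/20) and 82-83% for four. An arm-by-factor test would give about 5% false signals per factor, and about 26% for at least one of six.

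These figures rest on assumed event shares, on a true HR of 0.625 in everyone, and on 210 PFS events. The 26% also assumes that the factors are independent, which is only approximate because the refractory-status groupings overlap. No equivalent was computed for OS, since the plan states no OS effect size. The primary PFS comparison is unaffected. Severity is minor.

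**What to change.** - For each planned subgroup factor, fit a Cox model for PFS and for OS with arm, factor and arm-by-factor term, as already planned for region.
- Report the interaction estimate (ratio of HRs), its 95% CI and one p-value per factor beside the subgroup HRs and CIs. A factor with more than two groups needs a ratio for each group against a reference and one joint test.
- Drop the within-subgroup LR and HR p-values from the PFS and OS shells in 11.3.6 to 11.3.11.
- Define the p-value in 11.3.4.8 as the arm-by-factor test, from Cox models for PFS and OS and from logistic models for response rate.
- State that the analyses are exploratory and that a non-significant interaction does not show a uniform effect, giving the power figures (about 66% for a ratio of HRs of 0.5 and 36% for 0.625, with equal halves).

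The cost is a few model terms and a changed column; no new data are needed. If the tables have already been produced, the interaction results can be added and labelled as added later. The main drawback is low interaction power, which is why the estimate and CI should accompany the p-value.

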8.8 Methods for handling missing data

Missing values will be tabulated with their frequency but they will not be included in the calculation of percentages.

8.9 Interim and group sequential analyses

See details of the interim analyses and stopping rules in sections 5.1 and 6.1.

8.10 Data analysis for the Independent Data Monitoring Committee

These analyses will be specified in the independent data monitoring committee charter, in a separate document.

8.11 Identification of fixed or random effects models

Not applicable

8.12 Analyses of the effects of plitidepsin on the QTc interval

A substudy will be conducted to assess the potential effects of plitidepsin on the QTc interval of patients with relapsed/refractory multiple myeloma enrolled in clinical trial APL-C-001-09. These analyses will be specified in a separate document.

8.13 Analyses of performance status as an index of quality of life

Since patient reported outcome questionnaires have not been collected in this study, indirect measures of improvement like time to first performance status deterioration will be analyzed according to the Kaplan-Meier method.

9 STATISTICAL SOFTWARE

EAST v5.2 has been used to calculate sample size. SAS v9 (4) will be used for all statistical analysis outputs. Stata v14 or greater will be used for the analysis of crossover by RPSFT method.

APPENDIX I

All tables will be created at the time of each analysis planned in the protocol if applicable, and at study end.

10 Study Patients

10.1 Patient disposition

Main characteristics concerning inclusion in the study, patient crossover from arm B to arm A, withdrawal from the study and protocol deviations will be displayed in this section.

Table 10.1.1 Number of patients included, treated and evaluable for the main endpoint.

	Arm A		Arm B		Total	
	N	%	N	%	N	%
All Randomized Patients						
Eligible patients*						
All Treated Patients						
All Evaluable Patients						
All Crossover Patients	NA	NA				

(*)Patients meeting all inclusion criteria and not meeting any exclusion criteria.

Listing 10.1.2 Patients randomly assigned to one treatment arm and treated in the other one by mistake

Patient id.	Assigned arm by randomization	Treatment received
...		

Listing 10.1.2a Patients assigned to the wrong stratum by mistake

Patient id.	Assigned stratum by randomization	Actual stratification values
...		

Listing 10.1.2b Comparison of Durie-Salmon at IVRS and baseline value

Patient id.	Durie-Salmon value at IVRS	Actual Durie-Salmon value
...		

Listing 10.1.2c Comparison of ECOG PS at IVRS and baseline value

Patient id.	PS ECOG value at screening	PS ECOG value at IVRS	Last ECOG before start of study treatment
...			

Table 10.1.3 Patients accrual by institution

			Arm A	Arm B	Total
No. included	Country 1	Institution 1			
		...			
		Total			
	...	Institution 1			
		...			
		Total			
	Total	Institution 1			
		...			
		Total			
No. treated	Country 1	Institution 1			
		...			
		Total			
	...	Institution 1			
		...			
		Total			
	Total	Institution 1			
		...			
		Total			

Table 10.1.4 Study dates

	Arm A	Arm B	Total
Date of first randomization			
Date of first dose of the first patient			
Date of last randomization			
Date of first dose of the last patient			
Date of last dose			
Date of last follow-up*			

(*) Last follow-up or exam or procedure before clinical cut-off or study closure

Table 10.1.5 Last cycle in Arm A before crossover

Last cycle before crossover	Crossover patients	
	N	%
Cycle 1	X	XX.X
Cycle 2		
...		
Total		

10.2 Reasons for treatment discontinuation

Table 10.2.1 Study discontinuation

Reason	Arm A		Arm B		Total	
	N	%	N	%	N	%
End of study (study stopped)						
Patient refusal						
Never treated*						
Death (due to toxicity)**						
Death (non-treatment-related)***						
Investigator decision						
Other ****						
Lost to follow-up						
Total						

(*) See Listing 10.2.3 (**) Cause of death = Toxicity (study drug related) (***) Cause of death = Malignant disease or Other (****) See Listing 10.2.2

Listing 10.2.2 Study discontinuation due to other reason

Arm	Patient id.	Specify
...		

Listing 10.2.3 Patients randomized but not treated

Arm	Patient id.	Off-study reason
...		

Table 10.2.4 Treatment discontinuation

Reason	Arm A		Arm B		Total	
	N	%	N	%	N	%
Progressive disease						
Toxicity						
Patient refusal						
Investigator decision						
Death (due to toxicity)*						
Death (non-treatment-related)**						
Other ***						
Total						

(*) Cause of death = Toxicity (study drug related) (**) Cause of death = Malignant disease or Other (***) Specify (see listing 10.2.6)

Table 10.2.5 Reasons for treatment discontinuation by cycles received

Reason	Arm A				Arm B				Total			
	Last cycle				Last cycle				Last cycle			
	1	2	... ****	Total	1	2	...	Total	1	2	...	Total
Progressive disease												
Toxicity												
Patient refusal												
Investigator decision												
Death (due to toxicity)*												
Death (non-treatment-related)**												
Other ***												
Total												

(*) Cause of death = Toxicity (study drug related) (**) Cause of death = Malignant disease or Other (***) Specify (see listing 10.2.6) (****) Cycles > % will be grouped as 6-10, 10-20 and >20.

When reason for discontinuation is toxicity or study treatment-related death, identify patients and describe them in depth here.

Listing 10.2.6 Reasons for treatment discontinuation other than progressive disease.

Arm	Patient id.	Reason	Last cycle	Comments
...				

Listing 10.2.7 Treatment discontinuation due to AEs

Arm	Patient id.	Cycle	Preferred term code	Adverse event reported (verbatim)	Grade	Relationship	Onset date	Resolved date	Significant consequences
...									

Action taken: study drug withdrawal

